Research Team. [name] is a relatively new faculty member to the University of Michigan and is the PI on the two NIH funded projects. [name] has developed an extensive, evidence-based intervention (CHAMP) that has strong preliminary data. [name] is the PI on the Parent Award R01 (R01HL132979-01) and a motor developmentalist and pediatric exercise scientist who developed CHAMP and has extensive experience in the implementation of interventions in early childhood and school-based settings in racial/ethnic minority groups. She served as the PI/Co-I on funded projects (federal and private) projects (R03-NICHD, R01-NHLBI, Robert Wood Johnson Foundation). She has also received additional research and hands-on didactic training in developing a sustainable independent

Table 1. Foundations of CHAMP Intervention and Links to SR.

TARGET Structure	Use of TARGET Structure in CHAMP to Promote Self Regulation Skills
Task: provide variety of tasks that range in level of difficulty to meet the skill level/ability and needs/ interests of the learner	Self-select from a range of task/activities that range in difficulty (create goals and strategies, plan and implement actions, make decisions, self-manage, self-monitor, and self-correct behavior)
Authority: fostered by allowing children to actively participate in the decision-making process	Self-manage and self-monitor behaviors (create goals and strategies, plan and implement actions, make decisions, self-manage, self-monitor, and self-correct behavior, manage emotions, understand and appropriately navigate social environments)
Evaluation/Recognition: avoids social comparison, recognize progress and improvement	Self-evaluate own performance (self-monitor behaviors, self-reflection of progress, manage emotions)
Grouping: focuses on grouping patterns. Children are not grouped, but given the opportunity to self-select their engagement	Self-select own engagement in task; give child ability to self-govern learning experience (plan actions and make decisions, self-monitor behavior, self-correct behaviors, manage emotions, appropriately navigate social environments, collaborative efforts)
Time: individualized instruction and learning experience.	Self-direct own learning (plan actions and make decisions, self-monitor behaviors, self-correct behaviors, manage emotions)

Figure 2. Conceptual Model: Self-Regulation as a Mechanism of Change in CHAMP.

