Theoretical Foundation and Intervention Approach. The Children's Health Activity and Motor Program (CHAMP) is grounded in Achievement Goal Theory³⁷⁻³⁸ and adheres to the TARGET structures – task, authority, recognition, grouping, evaluation, and time;^{40, 41; Table 1} Achievement Goal Theory refers to our beliefs, attributions, and affect that contribute to our behaviors and represents the way individuals approach, engage, and respond to educational and classroom-based activities³⁷⁻³⁸. This evidence-based intervention that the PI developed as part of her dissertation in 2007. Data supports that the theoretically-grounded approach enhances both motivation and movement behaviors of the child and promotes MC, PMC, PA, and movement knowledge (see PI [name] work^{10, 12-13, 16, 42-43} and Preliminary Data section C.3). CHAMP focuses on the process of learning and skill mastery.^{37,38} CHAMP provides children the opportunity to navigate the movement environment they deem appropriate for their own level of development.^{10, 16, 38, 38} For example, CHAMP provides a range of movement activities with varying levels of difficulties to accommodate a range of developmental levels (see provided CHAMP example). Additionally, CHAMP focuses on the process of learning motor skills rather than the product (outcome)

of learning motor skills, which aligns with early childhood principles of development and learning¹⁹ and with the best practices of motor development.³⁹ The focus on developmental processes targets children's intrinsic motivation and persistence reinforces learning; thus, this intervention promotes children's PMC and continued development of MC and PMC, beyond the specific intervention process.³⁷⁻³⁸ Three theoretical tenets are crucial to CHAMP^{37,38,40,41}:

- a) **The relationship between effort and personal progress.** CHAMP promotes personal effort, progress, and improvement of skills. Effort and progress help young children build patterns of achievement behavior that have positive long-term implications for learning and persistence in activities across the lifespan.
- b) **Learners' self-selection of tasks.** Learners select tasks that effectively challenge their ability and enhance their competence, which leads to confidence in their capability to succeed on other skills.

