The Children's Health Activity Motor Program (CHAMP) Implementation. CHAMP will be implemented during the scheduled movement sessions at each participating preschool (see preschool letters of support, Appendix A). CHAMP consists of (4, 30-minute classes a week or 3, 40-minute classes a week, based on the needs of the school schedule). ~~~30 weeks per year that will equate to ~3600 minutes of intervention time (30 min sessions X 4 days per week X 30 weeks per year)~~. Each session will consist of three parts: (a) 2 -3 min of motor skill introductory activity, (b) 25 min of motor skill instruction and practice, and (c) 2 -3 min motor skill closure activity. The control condition will be the preschools typical activity programs (i.e., outdoor/freeplay recess) and will be implemented according to the existing procedures within the preschool center. The centers outdoor program consist of outdoor free-play activity on a large playground area with a variety of play structures (swings, slides, ladders) that promote gross movement and activity in preschoolers. For the control condition, there will be no planned instruction nor activities provided by the classroom teachers. CHAMP will be implemented by two trained movement science specialists (1 instructor and 1 assistant). Instructors will attend a 3-day (4 hr/day) workshop/training session prior to the start of the intervention. The training workshops will be conducted by [name], an expert in movement/physical activity programming in early childhood settings and the developer of CHAMP. During the training workshops, instructors will learn the theoretical approach of CHAMP, see and actively participate in a CHAMP session and demonstrate effective implementation of the CHAMP intervention. During the training session, instructors must be able to provide a range of cues and prompts to promote skill learning, set up and demonstrate basic task progressions for motor skills, modify tasks based upon the child's present level of performance and rates of improvement, and implement CHAMP with fidelity, appropriate transitions and pacing, while ensuring safety. All training sessions will be digitally recorded and available through a private YouTube channel. A printed manual will also be provided to promote fidelity of the intervention. During the intervention, instructors will wear wireless microphones and digitally record each CHAMP session in order to determine fidelity. Ensuring fidelity demonstrates a measure for the internal validity of CHAMP.⁴⁴ Fidelity will be calculated from the digital recordings using a systematic observation tool established for mastery interventions.⁴⁵ CHAMP fidelity checks will be conducted during week 1, 3, 7, 15, and 25. [name] will deliver fidelity support (additional training) to instructors by providing adjustments to teacher behaviors if CHAMP specialists are not implementing CHAMP with fidelity. Concurrently, during weeks 1, 3, 7, 15 and 25, systematic observations tools at the control site will also occur for additional internal validity.⁴⁶

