children's participation over the course of the study, we will provide \$10 gift cards to each child for each successful data collection and accelerometer return in year 1 (2 times) and during the follow-up assessments. Additional incentives will also be provided to children for their participation (e.g., pencils, stickers, wristbands, etc.). To further maintain the necessary sample size, we will contact children (via parental contact information) that have relocated within the immediate area and conduct a home visit or University visit to continue testing. The same participant incentives will be provided for relocated children who continue testing.

Variables and data sources. This section describes the variables of interest and their data source. All data will be collected by trained individuals that are blind to the purpose of the study. The preschool personnel/staff have no role in data collection.

1. **Demographics.** Date of birth, sex, and race/ethnicity will be collected as supporting demographical information and collected through self-report through the IRB consenting process by the parent/guardian. Upon return and to compensate the parent/guardian for their time, parent/guardian will receive a one-time \$5.00 cash incentive.

Time Frame: Measured at baseline (Month 0).

2. **Body Composition.** Body composition will be calculated using standing height will be recorded on a SECA 769 to the nearest 0.1 cm. Weight (mass) will be rounded to the nearest 0.1 kg using a digital scale. Researchers will assist preschoolers in removing their shoes and socks. Students would stand still on the appropriate scale to complete the assessment. Waist circumference will be assessed with a non-elastic plastic tape measure. The tape measure will be placed around your child's waist in a standing position. Two measures will be taken and the average of the two will be used for data analyses. Preschoolers will complete the body composition assessments in small groups of 4 – 6 and should take 12 – 15 minutes to remove/put on shoes/socks and take the assessment for each group. The assessment will be completed in a designated classroom/area at the child care center. This measure will be collected first as height and weight information along with birthdate and sex are needed for the calibration of the physical activity monitoring devices (Previously approved in PROTOCOL HUM00108917, HUM0011789).

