Time Frame: Measured at baseline (Month 0), post-intervention (month 9), and follow-up assessments at the end of years 2, 3, and 4.

3. **Motor Competence (MC).** All MC measures will be evaluated in an indoor space (i.e., gymnasium or designated indoor activity space) during the time allocated for movement and physical activity. As recommended to increase the predictive validity of MC for physical activity, we will assess MC using multiple measures of MC that include both process and product measures.⁶ All measures will be assessed concurrently.

Time Frame: Measured at baseline (Month 0), post-intervention (month 9), and follow-up assessments at the end of years 2, 3, and 4.

A. Process measure. The Test of Gross Motor Development (TGMD)⁵⁰ will be used to assess motor skill development and learning. The TGMD is a measure of fundamental motor skill competence in children ages 3 to 10 years and consists of locomotor (run, jump, gallop, slide, hop, leap, and skip) and object control skills (throw, catch, dribble, underhand throw, kick, one-handed forearm strike, roll, and two-handed strike off a tee). Scores for the two subscales (locomotor and object-control) of the TGMD will be reported as raw scores for each skill. Mean test-retest reliability coefficients were reported as .88 for locomotor items and .93 for object-control items.⁵⁰ Interrater reliability coefficients for both subscales were reported as .98.⁵⁰ The TGMD will be videotaped with digital video cameras by trained researchers. All TGMD videos will be coded by in the CMAH Lab under the direction of PI [name]. Specifically, PI [name] and

an approved research staff member will complete the video analyses. Inter-rater reliability will be established by another approved research staff member and Co-I [name], the developer of the TGMD will be available to consult if there are any issues on concerns. An overall score for total MC of 0 – 100 will be used for data analyses. (Previously approved in PROTOCOL HUM00108917, HUM0011789).

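### TGMD videos are to be scored by the PI, who developed CHAMP, and no procedure masks coders to arm, so the arm difference in process-measured motor competence is open to rater bias

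*Protocol*

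**What the plan says.** **Who scores.** Protocol, D. Methods, Variables and data sources, item 3.A (Process measure): "All TGMD videos will be coded by in the CMAH Lab under the direction of PI". The next sentence names the PI together with a second person: "an approved research staff member will complete the video analyses". For agreement, "Inter-rater reliability will be established by another approved research staff member". The same paragraph gives a total motor competence (MC) score of 0 to 100 for analysis.

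**Who the scorer is.** The Research Team section describes the PI as "a motor developmentalist and pediatric exercise scientist who developed CHAMP". The Theoretical Foundation section says of CHAMP: "This evidence-based intervention that the PI developed as part of her dissertation in 2007". Under CHAMP Implementation, the instructor workshops are run by "an expert in movement/physical activity programming in early childhood settings and the developer of CHAMP", and instructors "digitally record each CHAMP session in order to determine fidelity".

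**Contact with the children.** The consent sections place the PI at registration, Welcome Night, and drop-off and pick-up, and list the PI among the staff who may attend home visits. In the passage on re-assent, the team says that it will be at the sites regularly and will know the families and children well.

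**What is said on blinding.** The opening of Variables and data sources states: "All data will be collected by trained individuals that are blind to the purpose of the study". The Data Collection paragraph says that graduate students outside intervention delivery collect the data. The SAP's only blinded role is a check of 30% of data, in the Data Management text of the self-regulation supplement. Neither document describes masking of video coders to arm, coding of clips, or a scoring order.

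**The concern.** TGMD process scoring is a judgement made from video. The person named first to make it developed the intervention, trains its instructors by role, and belongs to a team that expects to know the children. Classes are the randomised units, so knowing a child's class can reveal the arm. If the scorer's expectation lifts scores in CHAMP relative to control, the shift enters the arm difference directly. Covariate adjustment, random effects and multiple imputation do not remove it.

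MC is one of the three outcomes in Hypotheses 1 and 2, so a false or inflated CHAMP effect on process-measured MC is what is at stake. An inter-rater check does not protect against this. It measures agreement, and two unmasked members of one lab can agree closely while sharing the same shift. The published reliability of .98 that the protocol cites says nothing about a difference by arm.

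**Working it through.** **Step 1. Set the statements side by side.**

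| Statement | Covers TGMD scoring? |
|---|---|
| Graduate students outside delivery collect data (Data Collection) | No. It concerns field collection. |
| Collectors are blind to the study's purpose (Variables and data sources) | If it covers collection only, scoring has no masking statement. If it covers scoring too, it conflicts with item 3.A, because the PI cannot be blind to the purpose of the trial. |
| A blinded member checks 30% of data (SAP, self-regulation supplement) | No. It is a data check for other measures. |
| A second staff member establishes inter-rater reliability (item 3.A) | It covers agreement. Masking is not stated. |

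On either reading of the second row, no arm masking of TGMD coders is described.

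**Step 2. What the bias can reach.**
- Accelerometer MVPA is not rated by a person and is not reached.
- Product measures (radar velocity, jump distance, catches, digitised stride measures) rest less on judgement and are less exposed.
- Aim 3, as stated, concerns PMC as mediator between MC and PA. Let the recorded score be MC + δ × arm, with δ constant. Within an arm δ is a constant, so the variance of MC and its covariances with PMC and PA do not change, and neither do the slopes. A pooled model with an arm term absorbs δ in that term. The slopes move only if arms are pooled without an arm term, or if the bias varies within an arm.

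**Step 3. Illustration of size.** The documents give no figure for rater bias, so the shifts below are assumptions.

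Sample size: the protocol's 106 per arm was derived for PA (difference 12.1, SD 27, 90% power, alpha 0.05). The normal approximation gives 2 × (1.960 + 1.282)² × (27/12.1)² = 104.6, that is 105. The t-test version gives 105.6, that is 106, so the stated figure reproduces. It is used here only as a plausible number of analysed children.

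Method, with no true effect and a shift of b SD in the whole score:
- children per class m = 212/30 = 7.07
- design effect = 1 + (m − 1) × ICC
- effective n per arm = 106 / design effect
- noncentrality = b × √(effective n / 2)
- rejection rate from the noncentral t, both tails, with 210 df at ICC 0 and 28 df (30 classes − 2) otherwise

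| ICC | Design effect | Effective n per arm | Critical t | b = 0.1 | b = 0.2 | b = 0.3 |
|---|---|---|---|---|---|---|
| 0 | 1.00 | 106.0 | 1.971 | 11% | 31% | 58% |
| 0.05 | 1.30 | 81.3 | 2.048 | 9% | 23% | 46% |
| 0.3 | 2.82 | 37.6 | 2.048 | 7% | 13% | 24% |

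Example: at ICC 0.05 and b = 0.2, noncentrality is 0.2 × √(81.3/2) = 1.275, and the rejection rate is 23%. The nominal rate is 5% throughout. The ICC for MC is not given. The value 0.3 is the SAP's assumption for the self-regulation measures only.

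**The case against.** The strongest reply is that knowing a study's purpose is not the same as knowing the arm behind a clip. The videos are filmed in testing sessions, collectors are outside delivery, and nothing says that files carry arm or class labels. The documents do not say who reviews the fidelity recordings, and the public text does not show who gives instructors corrective support. This reply stands against one tempting inference, that masking is impossible under this plan. The documents support only that masking is undescribed, and that it is hard to credit for a scorer with these roles.

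Three further points stand:
- A reader might take MC for the trial's lead endpoint. It is not: the sample size rests on change in PA, and the accelerometer section names MVPA as the primary outcome.
- A reader might also infer that Aim 3 is biased as a matter of course because MC is its exposure. A constant shift within arm leaves those slopes alone (Step 2).
- The PI is one of two coders and the split of videos is not given, so applying the shift to the whole score may overstate its effect.

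The reply does not dispose of the point. The scorer is named, the roles are legible in the public text, and no procedure is given that would separate the scorer's expectations from the scores.

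**Conclusion.** The concern holds for process-measured MC in Aims 1 and 2. The plan gives a judgement-based outcome to the developer of the intervention, describes no masking to arm, and makes a blinding statement that either omits scoring or conflicts with it. This should be corrected, but it does not threaten the MVPA endpoint. Product-measured MC is less exposed. Aim 3 is affected only under the conditions in Step 2.

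Neither the direction nor the size of any bias can be known from the documents. Under assumed shifts of 0.1 to 0.3 SD, false rejection runs from 11% to 58% at ICC 0 and from 7% to 24% at ICC 0.3. These figures assume 106 analysed children per arm, 30 equal classes, no true effect, and a shift that applies to every score in one arm relative to the other.

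**What to change.** Amend item 3.A and the blinding statement in the protocol:

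- Primary TGMD scores come from approved lab staff with no part in CHAMP training, delivery or fidelity review.
- Clips carry random codes with no arm, class or site label.
- Both arms are scored in mixed random order within each assessment wave. Mixing clips across all waves would hold scoring until the last follow-up, and so delay Aim 1 and the yearly reports promised to parents.
- The PI is limited to coder training and to adjudication of coded clips.
- The blinding statement says that masking to arm covers scoring as well as collection.
- Product measures are reported beside the TGMD score as a cross-check.

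The cost is a file-coding and shuffling step, and moving the PI's coding hours to staff. The documents do not confirm that the approved staff are uninvolved in delivery, so the sponsor would have to assign coders with that in mind. No extra child contact is needed, because scoring is from stored video. Masking will remain imperfect, since the children are visible on the clips.
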